### **12.5.3 Interim Analysis (IA)**

One interim analysis is planned to be conducted for this study. This interim analysis will be primarily for sample size recalculation of the Part II study. The study will not be stopped due to the efficacy results, and no hypotheses testing will be conducted in this IA to assess the differences between the two groups.

This interim analysis is planned to be conducted when 50% of subjects are randomized and completed the Week 24 post-operative follow up evaluations.

The interim analysis will be conducted under the auspices of an independent Data Safety Monitoring Board (DSMB).

There is no intention of decreasing the sample size; however, the sample size may be increased to either establish the non-inferiority and/or may be increased sufficiently to establish superiority depending on the results of the interim analysis.

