#### 4. TABLE 3: STUDY FLOWCHART AND FOLLOW-UP ASSESSMENTS

Procedure	Screening/ Baseline	Surgery	Post-Operative Follow-up Evaluation						
	Visit 1	Visit 2	Visit 3	Visit 4	Visit 5	Visit 6	Visit 7	Visit 8	Visit 9
	Day -21 to -1	Day 0	Day 10 ±3 Days	Wk 6 ± 5 Days	Wk 12 ± 7 Days	Wk 24 ± 14 Days	Wk 36 ±14 Days	Wk 52 ±28 Days	Wk 104 ±56 Days
Informed Consent	X 								
Medical History & Demographics	X								
Subject Eligibility Verification	X	X							
Physical Assessment - Knee	X		X	X	X	X	X	X	X
Magnetic Resonance Imaging (MRI)	X 		X					X	X
Weight bearing AP / Lateral / Merchant View	X								
Weight-bearing posteroanterior radiograph	X								
Standing Long Leg Alignment	X							X	
International Cartilage Repair Society classification (ICRS)		X 	X 					X 	X 
International Knee Documentation Committee (IKDC) 	X			X 	X	X	X	X	X
Visual Analogue Scale (VAS), knee pain	X		X	X	X	X	X	X	X
Knee Injury and Osteoarthritis Outcome Score (KOOS)	X			X	X	X	X	X	X
SF-12	X			X	X	X	X	X	X
EQ-5D-5L	X		X	X	X	X	X	X	X
Subject Satisfaction								X	X

Adverse Events		X	X	X	X	X	X	X	X
Post-operative Rehabilitation 			X	X					
Concomitant Medications	X		X	X	X	X	X	X	X
Protocol Deviations	X	X	X	X	X	X	X	X	X

 Must occur prior to any study-specific procedures

 MRI must occur within 9 months of enrollment into this study confirming presence of a medial femoral chondral lesion and medial meniscal tear requiring a partial meniscectomy

 International Cartilage Repair Society (ICRS) classification will be used for intra-operative arthroscopic confirmation of the lesion grade

 International Cartilage Repair Society (ICRS) classification will be used for determination of lesion grade by MRI

 International Knee Documentation Committee (IKDC) Subject Knee Evaluation and Knee Examination Forms will be used

 IKDC Knee Examination Form - Subject dependent

 Post-operative Rehabilitation per Investigator standard of care

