## 8. STUDY ENDPOINTS

### 8.1 Primary Endpoint

The primary endpoint is to evaluate the change in Knee and Osteoarthritis Outcomes Scores (KOOS) scores at Week 52 post-operative compared to baseline.

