### **12.2.2 Secondary Endpoints:**

There are two sets of endpoints that are known and well established in this patient population, the clinical and imaging endpoints. Both of these will be assessed in this protocol.

- Clinical Endpoints
  - Change in International Knee Documentation Committee (IKDC) Subjective Knee Evaluation Form scores from baseline
  - Change in International Knee Documentation Committee (IKDC) Knee Examination Form scores from baseline
  - Change in KOOS scores from baseline at Weeks 6, 12, 24, 36 and 104
  - Change in Visual Analogue Scale (VAS) scores from baseline
  - Change in SF-12 scores from baseline
  - Change in the EQ-5D-5L scores from baseline
  - Subject Satisfaction at Weeks 52 and 104
- Imaging Endpoints
  - MRI assessments at Day 10, Weeks 52 and 104
  - ICRS grade of chondral lesion at Day 10, Weeks 52 and 104

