### 12.5.3.1 Procedures for Interim Analysis

The data to be used in the interim analysis and the treatment assignment of each randomized subject will be given to the independent statistician. Using this data, the independent statistician will calculate the following metrics for the primary end point:

- difference in change in KOOS scores between the treatment groups
- change in KOOS score from baseline in Group I and the observed number of subjects in the group
- change in KOOS score from baseline in Group II and the observed number of subjects in the group
- dropout rate at the time of the IA
- statistical power of the study at the time of the Interim Analysis (using a conditional power approach)
- conditional power in this IA (CP) will be calculated according to the following formula (Chen 2004 [11]) using primary endpoint data from the ITT population.

$$CP(f_1, z_1) = \Phi \left\{ z_1 / \sqrt{f_1(1-f_1)} - z_\alpha / \sqrt{(1-f_1)} \right\}$$

Where:

- $CP(f_1, z_1)$  is the conditional power at the IA
- $\Phi\{\cdot\}$  is the cumulative distribution function of a standard Normal distribution ( $\mu=0$ ,  $\sigma^2=1$ )
- $f_1$  is the fraction of patients enrolled and used in the interim analysis before decision of increasing the sample size
- $z_\alpha$  is the upper  $\alpha$  quintile for standard Normal distribution
- $z_1$  is the standardized Normal

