### 12.5.3.2 Rules and Method for Increasing Sample Size

The sample size will be adjusted only if the conditional power at the time of the Interim Analysis is 50% or more and less than 80%. The sample size will be recalculated based on the observed difference between the treatment groups.

If the conditional power is larger than 50%, then the sample size will be adjusted upward and no Type I error rate adjustment will be made to the final analysis.

If the conditional power is less than 50%, the Type I error rate will be inflated and statistical adjustment will be made to the final analysis, an adjustment to the final p-value will be made as follows:

$$p\text{-value} = 2 [ 1 - \Phi \{ | f_2^{1/2} z_1 + (1-f_2)^{1/2} z_2 | \} ]$$

where:

P-value is the adjusted target p-value at the end of the study reflecting the adjustment for increasing the study size at the interim analysis

$n_1$ , is the sample size at the time of the interim analysis ( $n_1 = n_{gp1} + n_{gp2}$ )

$n_2$  is the re-calculated sample size to be enrolled after the interim analysis

$f_2 = n_1 / (n_1 + n_2)$  is the fraction of the newly planned sample size at the IA

$z_1$  is the observed z score at the time of the interim analysis

$z_2$  is the observed z value of the z score only based on the data collected after the interim analysis

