### **12.7.5 Efficacy Analyses**

#### ***12.7.5.1 Primary Analysis***

##### Primary Endpoint:

The primary analysis will be conducted on the Intent-to-treat (ITT) population. The change in Knee and Osteoarthritis Outcomes Scores (KOOS) from baseline will be compared between the device/treatment groups using Repeated Measures Analysis of Covariance.

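### The only interim is triggered at Week 24, but its conditional power is defined on Week 52 KOOS, and the rules for acting on the result conflict

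*Protocol*

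**What the plan says.** **Timing.** Protocol section 12.5.3 plans one interim, mainly to recalculate the sample size: "This interim analysis is planned to be conducted when 50% of subjects are randomized and completed the Week 24 post-operative follow up evaluations". With 82 randomized subjects (section 12.3), that is 41.

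**Data used.** Section 12.5.3.1 lists its metrics for the primary endpoint and computes conditional power (CP) "using primary endpoint data from the ITT population". Section 8.1 defines that endpoint as the change in KOOS "scores at Week 52 post-operative compared to baseline". Week 24 appears only among the secondary endpoints of section 12.2.2: "Change in KOOS scores from baseline at Weeks 6, 12, 24, 36 and 104". Under section 12.7.5.1, KOOS change "will be compared between the device/treatment groups using Repeated Measures Analysis of Covariance".

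**Information fraction.** In the CP formula, f1 "is the fraction of patients enrolled and used in the interim analysis before decision of increasing the sample size". The statistic z1 is described only as a standardized Normal, and the α behind the critical value is not given at that point. Section 12.3 uses a two-sided 0.05 test and an 8-point non-inferiority margin.

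**Rules (section 12.5.3.2).**
1. The number of subjects "will be adjusted only if the conditional power at the time of the Interim Analysis is 50% or more and less than 80" per cent.
2. If CP exceeds 50%, the sample size goes up with no Type I error adjustment. No upper limit is given.
3. If CP is below 50%, the final p-value is adjusted. The adjustment is described as one for having increased the study at the interim.

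**The concern.** The 50% and 80% cut-offs decide whether the trial is enlarged, so the CP behind them must be well defined. The trigger and the data source do not fit together, because a subject who has just completed Week 24 is 28 weeks short of the primary outcome. The independent statistician, holding unblinded data, would have to choose between the available Week 52 completers, Week 24 KOOS as a stand-in, or a model-based Week 52 estimate. These can lead to different sample-size decisions.

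The rules then give conflicting instructions below 50% and, less firmly, at 80% and above. At stake are the sample-size decision and, if the trial is enlarged below 50%, the validity of the final p-value.

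**Working it through.** **1. The plan's own figures.** 70/(1 − 0.15) = 82.4; the plan uses 82. Half of 82 is 41, so f1 = 41/82 = 0.5 if all 41 are counted.

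**2. Week 52 data at the trigger.** The protocol gives no accrual rate. Assume r subjects per week, uniform accrual and no dropout. When the 41st subject reaches Week 24, the number at Week 52 is max(0, 41 − 28r).

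| Accrual of 82 over | r | With Week 52 data | Fraction of 82 |
|---|---|---|---|
| 52 weeks | 1.58 | 0 | 0 |
| 104 weeks | 0.79 | 18.9 | 0.23 |
| 156 weeks | 0.53 | 26.3 | 0.32 |
| 208 weeks | 0.39 | 30.0 | 0.37 |

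For any r above zero the count is below 41.

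**3. Cut-offs in the stated formula.** CP = Φ{z1/√(f1(1 − f1)) − 1.96/√(1 − f1)}. At f1 = 0.5, CP is 50% at z1 = 1.386 and 80% at z1 = 1.807. With 1.645 in place of 1.96 they would be 1.163 and 1.584, so the critical value needs stating.

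**4. Model-based Week 52 estimate with f1 = 0.5.** I computed the Week 52 information by generalised least squares on the KOOS visits available at the interim. Correlations were assumed: exchangeable or first-order autoregressive, 0.5 or 0.7. The fraction is 0.26 to 0.39 for 104-week accrual and 0.34 to 0.45 for 156-week accrual. With the correct fraction, a stated CP of 50% becomes 63–81% (104 weeks) or 55–69% (156 weeks). A stated 80% becomes 89–97% or 84–92%. At 52-week accrual the model has no Week 52 data.

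**5. Week 24 KOOS used directly, f1 = 0.5.** Let k be the ratio of the expected non-inferiority z at Week 52 to that at Week 24, and ρ the correlation between the two visits (assumed 0.5 to 0.8). The CP of the Week 52 test is Φ{(√2·k·z1 − 1.96)/√(0.5(1 − ρ²) + 0.5)}.

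| k | Calculated 50% is | Calculated 80% is |
|---|---|---|
| 0.75 | 28–30% | 48% |
| 11/12 | 42–43% | 66–68% |
| 1 | 50% | 74–77% |
| 1.25 | 70–72% | 91–93% |

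Because z1 contains the margin, k is not the ratio of treatment effects. With equal SDs, a benefit falling from 4 to 3 points gives k = (3 + 8)/(4 + 8) = 11/12.

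**6. Hypothesis behind z1.** Section 12.5.3 allows an increase for non-inferiority and/or superiority. Take an observed difference of zero and f1 = 0.5. Without the margin, z1 = 0 and CP = Φ(−2.77) = 0.3%. With the margin, back-solve the SD from section 12.3 assuming a true difference of zero: 8/{(1.96 + 0.84)√(2/35)} = 11.9. Then z1 = 8/{11.9√(2/20.5)} = 2.15 and CP is about 94%.

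**7. How often the rules conflict.** At the 80%-power alternative with f1 = 0.5, z1 has mean 2.80 × √0.5 = 1.98.
- P(CP < 50%) = Φ(1.386 − 1.98) = 0.28.
- P(CP ≥ 80%) = 1 − Φ(1.807 − 1.98) = 0.57.
- The remaining 0.15 is the only zone where the rules agree.

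**8. The correction below 50%.** The adjusted statistic is √f2·z1 + √(1 − f2)·z2, with f2 = n1/(n1 + n2) and n2 the re-calculated second-stage size. Write z1 = S1/√n1 and z2 = S2/√n2. The sum is then (S1 + S2)/√(n1 + n2), the ordinary pooled z. A numerical check with n1 = 41 and n2 = 90 gave 2.605 both ways.

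Simulation (4 million trials, f1 = 0.5, one-sided 0.025, size raised to restore 80% CP up to assumed caps of 1.5 to 5 times the planned size):
- Increase for any CP below 80%, stated formula: 0.029 to 0.035.
- The same, but only when z1 is positive: 0.027 to 0.030.
- Any CP below 80%, weights fixed at the planned 0.5: 0.025.
- Increase only for CP of 50% to below 80%, no correction: 0.025.

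**The case against.** **Week 24 may have been intended, and the protocol defers detail to a SAP.** The estimation model could reasonably sit there. But the protocol itself fixes the trigger, the data source, the formula, f1 and the cut-offs, and these do not fit together. Nothing says that Week 24 stands in for Week 52.

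**There may be usable Week 52 data.** This stands. A reader might infer that the interim would rest on few or no Week 52 outcomes. That depends on accrual, which the protocol does not give. What holds generally is that none are guaranteed and that the number at the trigger stays below 41. If f1 counts only Week 52 completers, the formula is also correct as it stands.

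**Using Week 24 could do little harm.** This also stands. A reader might infer that a calculated 80% is really about 48% if the effect shrinks by a quarter. That requires the whole non-inferiority z to shrink by a quarter. From a zero difference at Week 24, the study device would have to be 2 points worse by Week 52, since (−2 + 8)/8 = 0.75. Ratios above 1 move CP the other way.

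**The second rule can be read as limited by the first.** Fair: its new content is that no Type I error adjustment is made. The conflict at 80% or more is therefore loose drafting. That reading does not rescue the third rule, which corrects for an increase that the first rule forbids.

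**Conclusion.** Two defects are established from the text alone: the Week 24 trigger does not match the Week 52 data source for CP, and the below-50% branch contradicts the first sentence of section 12.5.3.2. The missing upper limit in the second rule is a weaker conflict. At the design alternative the firm conflict covers about 28% of interim results and the weaker one about 57%, taking f1 = 0.5 and a critical value of 1.96.

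The size of the CP error depends on accrual, correlations and the course of the effect. None of these is in the protocol, so those figures are illustrative.

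A reader might infer that the adaptive design inflates Type I error as a whole. The protocol does not support that: an increase confined to CP of 50% to below 80% keeps the one-sided rate at about 0.025 in the simulation. Inflation, to about 0.029–0.035 under the assumed caps, arises only if the trial is also enlarged below 50% and the stated correction is relied on. This should be fixed before the interim.

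**What to change.** **Section 12.5.3.1**
- Name the KOOS visit or model behind z1, for example the Week 52 difference from the repeated-measures model of section 12.7.5.1, using all KOOS visits available.
- State whether z1 tests non-inferiority (difference plus the 8-point margin) or superiority.
- Set f1 to the Week 52 information in that estimate, and state the critical value as 1.96.
- State what is done if too few subjects have Week 52 KOOS.
- If Week 24 KOOS is used instead, say so, state the assumption linking it to Week 52, and do not call the result the conditional power of the primary test.

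**Section 12.5.3.2**
- Give one action each for CP below 50%, 50% to below 80%, and 80% or more.
- Either delete the below-50% branch, or keep it with the stages split by subject and weights fixed at the originally planned sizes.

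**Cost.** Wording, a little more modelling by the independent statistician, and a stated interim information fraction below 0.5 (about 0.26 to 0.45 under the correlations and the 104- and 156-week accrual assumed above). Moving the trigger to Week 52 would remove the mismatch, but under uniform accrual over 104 weeks the 41st subject reaches Week 52 at 52 + 52 = 104 weeks, when enrollment ends.

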### 12.5.3.1 Procedures for Interim Analysis

The data to be used in the interim analysis and the treatment assignment of each randomized subject will be given to the independent statistician. Using this data, the independent statistician will calculate the following metrics for the primary end point:

- difference in change in KOOS scores between the treatment groups
- change in KOOS score from baseline in Group I and the observed number of subjects in the group
- change in KOOS score from baseline in Group II and the observed number of subjects in the group
- dropout rate at the time of the IA
- statistical power of the study at the time of the Interim Analysis (using a conditional power approach)
- conditional power in this IA (CP) will be calculated according to the following formula (Chen 2004 [11]) using primary endpoint data from the ITT population.

$$CP(f_1, z_1) = \Phi \left\{ z_1 / \sqrt{f_1(1-f_1)} - z_\alpha / \sqrt{(1-f_1)} \right\}$$

Where:

- $CP(f_1, z_1)$  is the conditional power at the IA
- $\Phi\{\cdot\}$  is the cumulative distribution function of a standard Normal distribution ( $\mu=0$ ,  $\sigma^2=1$ )
- $f_1$  is the fraction of patients enrolled and used in the interim analysis before decision of increasing the sample size
- $z_\alpha$  is the upper  $\alpha$  quintile for standard Normal distribution
- $z_1$  is the standardized Normal

### 12.5.3.2 Rules and Method for Increasing Sample Size

The sample size will be adjusted only if the conditional power at the time of the Interim Analysis is 50% or more and less than 80%. The sample size will be recalculated based on the observed difference between the treatment groups.

If the conditional power is larger than 50%, then the sample size will be adjusted upward and no Type I error rate adjustment will be made to the final analysis.

If the conditional power is less than 50%, the Type I error rate will be inflated and statistical adjustment will be made to the final analysis, an adjustment to the final p-value will be made as follows:

$$p\text{-value} = 2 [ 1 - \Phi \{ | f_2^{1/2} z_1 + (1-f_2)^{1/2} z_2 | \} ]$$

where:

P-value is the adjusted target p-value at the end of the study reflecting the adjustment for increasing the study size at the interim analysis

$n_1$ , is the sample size at the time of the interim analysis ( $n_1 = n_{gp1} + n_{gp2}$ )

$n_2$  is the re-calculated sample size to be enrolled after the interim analysis

$f_2 = n_1 / (n_1 + n_2)$  is the fraction of the newly planned sample size at the IA

$z_1$  is the observed z score at the time of the interim analysis

$z_2$  is the observed z value of the z score only based on the data collected after the interim analysis

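### Section 12.5.3.2 prints a p-value adjustment for a sample size increase that its own rule forbids, and the adjustment formula is the ordinary pooled test

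*Protocol*

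**What the plan says.** Protocol section 12.5.3.2 contains three statements about the trigger.

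- The size is "adjusted only if the conditional power at the time of the Interim Analysis is 50% or more and less than 80" percent. The basis for the new size is the difference seen between the groups at the interim.
- The second statement on the trigger reads: "If the conditional power is larger than 50%, then the sample size will be adjusted upward", with no Type I error adjustment. The 80% upper limit is not repeated here.
- The third statement reads: "If the conditional power is less than 50%, the Type I error rate will be inflated and statistical adjustment will be made". The final p-value is then 2[1 − Φ{|√f2·z1 + √(1−f2)·z2|}], described as "reflecting the adjustment for increasing the study size at the interim analysis".

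The weight is f2 = n1/(n1+n2), where n2 "is the re-calculated sample size to be enrolled after the interim analysis". The second-stage statistic z2 "is the observed z value of the z score only based on the data collected after the interim analysis".

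Section 12.5.3.1 gives the CP formula, in which f1 "is the fraction of patients enrolled and used in the interim analysis before decision of increasing the sample size". Section 12.5.3 places the interim analysis when half the subjects are randomized and have completed Week 24. The primary endpoint (section 12.2.1) is at Week 52.

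**The concern.** There are two faults.

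**The trigger contradicts itself.** The first rule excludes any increase below 50% CP. The later paragraph corrects the p-value for just such an increase. Sections 12.5.3 and 13.5 speak in general terms of raising the size or redesigning the study, but neither gives a rule for an increase below 50% CP.

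**The adjustment does not adjust.** Combining stage-wise z statistics protects the Type I error when the weights do not depend on the interim result. Here n2 is the re-calculated second-stage size, so f2 moves with the interim result and each stage gets the weight that simple pooling would give it.

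The protocol says the error will be inflated below 50% CP. Someone who raised the size there and followed the text would report an adjusted p-value that carries no correction. An SAP cannot repair this quietly: following the protocol inherits the fault, and departing from it contradicts the protocol.

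**Working it through.** **Inputs from the protocol.** Planned N = 82, 1:1 allocation, alpha 0.05 two-sided (0.025 in the direction of interest, zα = 1.96), and the interim at 50% of subjects, so n1 = 41 and f1 = 41/82 = 0.5. The stated 82 is consistent with 70 completers and 15% discontinuation: 70/0.85 = 82.4. The text gives no SD, but nothing below depends on one.

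**Assumptions.** z1 and z2 are independent. N is raised to reach 80% CP under the observed trend. N is capped at 2, 3 or 4 times 82, because the protocol states no maximum.

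**Step 1. CP boundaries.** From CP = Φ{z1/√(f1(1−f1)) − zα/√(1−f1)} with f1 = 0.5:

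- CP 10% at z1 = 0.745
- CP 50% at z1 = 1.96 × √0.5 = 1.386
- CP 80% at z1 = 1.807

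**Step 2. The printed statistic is the pooled z.** With unit SD and 1:1 allocation, the mean difference d1 from n1 subjects has variance 4/n1, so z1 = d1·√n1/2, and likewise z2 = d2·√n2/2. Then

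√f2·z1 + √(1−f2)·z2 = (n1·d1 + n2·d2) / (2√(n1+n2)),

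which is the z for the pooled difference. In 1,000 simulated data sets the two agreed to within 1.3 × 10⁻¹⁵. Under the planned repeated measures ANCOVA the identity is approximate.

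Example: n1 = 41, n2 raised from 41 to 123, z1 = 1.0, z2 = 2.0.

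- Printed formula: f2 = 41/164 = 0.25, Z = 0.5 × 1.0 + 0.866 × 2.0 = 2.232, two-sided p = 0.0256. The unadjusted test gives the same.
- Weight fixed at 0.5: Z = 0.7071 × (1.0 + 2.0) = 2.121, p = 0.0339.

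If N stays at 82, f2 = 41/82 = 0.5 and the printed formula is simply the planned test.

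**Step 3. One-sided Type I error.** The rejection probability given z1 is 1 − Φ{(zα − √w·z1)/√(1−w)}, with w = f2 (printed) or w = 0.5 (fixed). It is integrated over z1 ~ N(0,1). In every row N is raised at CP 50-80%. The new N is found by putting f = n1/N into the CP formula and solving for 80%. Below 50% CP, 80% is reachable within the cap only from z1 = 1.344 / 1.114 / 0.971, that is CP of 47% / 29% / 20%.

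| Action below 50% CP | Printed formula, cap 2× / 3× / 4× | Fixed weight 0.5 |
|---|---|---|
| None (first rule only) | 0.0245 / 0.0245 / 0.0245 | 0.0250 |
| N raised only where 80% CP is reachable | 0.0244 / 0.0243 / 0.0244 | 0.0250 |
| N raised where CP ≥ 10%, to the cap if 80% is unreachable | 0.0252 / 0.0251 / 0.0250 | 0.0250 |
| N raised for any z1 > 0, to the cap if 80% is unreachable | 0.0284 / 0.0291 / 0.0294 | 0.0250 |
| N raised at any z1, including z1 ≤ 0 | 0.0304 / 0.0326 / 0.0339 | 0.0250 |

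The last row lies outside a recalculation from the observed difference, since a difference of zero or less supports no finite N.

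**The case against.** The strongest reply is that the harm needs two departures from the text: ignoring the first rule, and sending N to a cap the protocol never mentions. Where the observed difference can support 80% CP, the error stays below nominal. Limited to CP of 10% or more, it is at most 0.0252. This stands, and it makes the matter chiefly one of a wrong and contradictory rule with modest inflation.

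A second reply is that the paragraph is a safeguard in case an increase is made anyway, for example on DSMB advice to redesign under section 13.5. That section gives no such rule, and the safeguard would not work, because its weights follow the re-calculated size.

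A third point concerns overlap. The interim follows Week 24 and the endpoint is Week 52, so z2 read literally could include Week 52 data from interim subjects. Then z1 and z2 are correlated, the statistic is not the pooled z, and the error figures do not apply. For illustration, an assumed correlation of 0.2 at equal weights gives 1 − Φ(1.96/√1.2) = 0.037 with no increase at all. The definition of n2 as subjects still to be enrolled favours separate subjects, but the text should say so. This limits the figures to the separate-subjects reading; it does not rescue the formula.

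The maximum size alone could be left to the SAP. Its absence is noted only because it leaves the inflation undetermined.

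**Conclusion.** The concern holds and should be fixed. The trigger and the CP < 50% paragraph cannot both apply, and the printed p-value is the unadjusted one under another name.

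If the 50-80% rule governs, one-sided error is 0.0245 and the paragraph has no purpose. If N is also raised below 50% CP on a positive observed difference, error is about 0.024 to 0.029 against 0.025, and whatever inflation arises is uncorrected. The size rests on independent stages, f1 = 0.5, an 80% CP target and the assumed caps. The contradiction and the lack of correction do not depend on the caps or the CP target.

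**What to change.** **Preferred.** State one trigger: increase only if CP is at least 50% and below 80%, otherwise keep 82. Delete the CP < 50% paragraph and its formula. Add the 80% limit to the sentence on upward adjustment. This costs wording only. At the effect giving 80% power at the planned size (E(z1) = 2.802 × √0.5), the rule gives 81.8% power with a mean N of 86.7.

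**If increases below 50% CP are intended:**

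- Fix the weight in advance at the originally planned information fraction of the interim cohort (0.5 if 41 of 82), in place of f2.
- Compute z1 from the subjects used at the interim and z2 only from the other subjects.
- State a maximum N.

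At the same effect, with N raised for any z1 > 0, power with fixed weights against the pooled test is 91.8% against 92.3% at a 2× cap, 93.4% against 93.4% at 3×, and 93.6% against 93.4% at 4×. The loss reaches about 1 point (92.9% against 93.9% at 2×) only if N is also raised at z1 ≤ 0. If the interim cohort differs from the planned fraction, the fixed weight loses some efficiency but keeps error control.

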### **12.3 Sample Size Determination, Power calculation, and Rationale**

[figure not shown]
This study will be conducted in a two parts. There is no power calculation for the Part I study. In the Part II study subjects will be randomized to one of the two treatment groups in a 1:1 ratio.

A total of 82 subjects (41 in the study device group and 41 in the control device group) will be randomized in an effort to assure that seventy (70) subjects (i.e., 35 subjects per group) complete the study.

PASS version 2011, is used for this sample size and power calculation. The requirement of 70 subjects (35 active and 35 control) is based on achieving 80% statistical power to detect a non-inferiority margin difference of 8 points between the two groups (10). For the same 80% statistical power, and significance level (alpha) of 0.05 two-sided test; one may choose different number of subjects depending on the expected and observed KOOS score and the acceptance of the non-inferiority delta. These are depicted in Figure 12-1 below.

The discontinuation rate is predicted to be no more than 15%. To accommodate the potential discontinuations, 82 randomized subjects (41 in the study device group and 41 in the control device) are needed for this study.

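### The adjusted final p-value defines stage 2 by enrolment for its weight but by data date for z2, so interim subjects can count twice and the p-value can be too small

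*Protocol*

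**What the plan says.** Section 12.5.3 of the protocol sets the timing: "This interim analysis is planned to be conducted when 50% of subjects are randomized and completed the Week 24 post-operative follow up evaluations". The primary endpoint (sections 8.1 and 12.2.1) is the change in KOOS from baseline to Week 52.

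Section 12.5.3.2 gives an adjusted final p-value for conditional power below 50%: p = 2[1 − Φ{|√f2·z1 + √(1−f2)·z2|}], with f2 = n1/(n1 + n2). Its terms are defined as follows:

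- n1 is the sample size at the interim, and z1 is the score observed then.
- n2 "is the re-calculated sample size to be enrolled after the interim analysis".
- z2 "is the observed z value of the z score only based on the data collected after the interim analysis".

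The same section permits a sample-size increase only when conditional power is at least 50% and below 80%. Section 12.5.3.1 says that conditional power uses primary endpoint data from the ITT population, and section 12.6.1 defines that population as everyone randomised. The error target in section 12.3 is a "significance level (alpha) of 0.05 two-sided test".

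**The concern.** The combination is standard normal under the null when z1 and z2 are independent and the weights are fixed in advance. The usual way to secure independence is to put each subject in exactly one stage. The protocol instead counts stage 2 by enrolment and measures it by when data arrive.

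Two groups fall between these definitions:

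- **Interim subjects still awaiting Week 52.** They were not enrolled after the interim, but they yield data after it. By the data-date rule they enter z2, having possibly already entered z1.
- **Subjects randomised but not yet analysed at the interim.** They also yield data only afterwards, but n2 does not count them. If n1 means only the subjects analysed, they are in neither count.

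No section assigns either group to a stage. At stake is the error rate of the p-value prescribed for the low conditional-power branch, or, on the other reading, the loss of randomised subjects from the final test.

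**Working it through.** **The plan's own figure.** Section 12.3 needs 70 completers and allows for 15% discontinuation: 70/0.85 = 82.35. The stated 82 reproduces within rounding (rounding up gives 83). No numerical result is given for the adjusted p-value; its target is 5% two-sided.

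**Inputs from the protocol.** 82 randomised; interim at 50%, so n1 = 41; two-sided alpha of 0.05.

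**Assumptions.** n2 = 41, so f2 = 41/82 = 0.5. z1 uses Week 24 KOOS. All k = 41 interim subjects give Week 52 data after the interim. Their Week 24 and Week 52 changes correlate at r = 0.5 to 0.8. z_α = 1.96.

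**Step 1: correlation of z1 and z2 under the data-date rule.** z2 then rests on k + n2 = 82 subjects.

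corr(z1, z2) = r·k/√(n1(k + n2)) = r × 41/√(41 × 82) = 0.707r.

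**Step 2: null variance of the combined score.**

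Var = 1 + 2√(f2(1−f2)) × corr = 1 + 0.707r.

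| r | Variance | SD | Two-sided error if always used |
|---|---|---|---|
| 0.5 | 1.354 | 1.163 | 9.2% |
| 0.7 | 1.495 | 1.223 | 10.9% |
| 0.8 | 1.566 | 1.251 | 11.7% |

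The last column is 2[1 − Φ(1.96/SD)].

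**Step 3: apply the branch rule.** Setting the formula in section 12.5.3.1 to 50% gives z1 = z_α√f1 = 1.96 × √0.5 = 1.386. The formula therefore applies when z1 < 1.386. Under the null that is Φ(1.386), or about 92% of trials. I simulated the trial with the combined score below that boundary and the Week 52 test on all 82 subjects above it.

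| r | Tail declaring RF worse | Tail favouring RF | Two-sided |
|---|---|---|---|
| 0.5 | 4.6% | 2.1% | 6.7% |
| 0.8 | 5.9% | 2.7% | 8.6% (8.5% before the tails are rounded) |

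The nominal values are 2.5%, 2.5% and 5%.

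**Step 4: less overlap.** With only 20 of the 41 interim subjects overlapping, the error if the formula is always used falls from 9.2% to 7.4% at r = 0.5, and from 10.9% to 8.3% at r = 0.7. If z1 uses only Week 52 values already in hand, k = 0, the correlation is 0 and the variance is 1.

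**Step 5: the enrolment-date reading.** If z2 uses only subjects enrolled after the interim, it is independent of z1. The squared weights f2 and 1 − f2 sum to 1, so with f2 fixed in advance the variance is 1 and the error is 5%. The cost is power. If m subjects are in neither stage and 82 give 80% power, power = Φ{(1.96 + 0.842)√((82−m)/82) − 1.96}. For assumed m = 10, 20 and 30 this gives 75%, 68% and 61%.

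**Step 6: split by subject.** With each randomised subject in one stage only and f2 fixed in advance, the correlation is 0 and the error is 5%.

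**The case against.** Several points on the other side stand.

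- A reader might infer that the p-value is invalid however stage 2 is read. The documents do not support that. Leaving already-randomised subjects out of both stages keeps z1 and z2 independent; it costs power and departs from ITT, but does not inflate the type I error. Nor must stage sizes match the weights: with independent scores and a fixed f2, a mismatch affects only efficiency.
- Week 24 is the trigger for the interim, not a stated visit for z1. Section 12.5.3.1 speaks of primary endpoint data, which could mean only Week 52 values in hand. The overlap then disappears, though n1 would no longer match the subjects who triggered the interim.
- If n1 means everyone randomised by the interim, nobody is missing from the counts.
- A reader might take 6.7% to 8.6% as the chance of a false claim for the device. It is not: the favourable tail stays near its nominal 2.5%.
- The section allows no increase below 50% conditional power, yet describes this p-value as an adjustment for an increase. As written, the formula may never follow an increase.

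The last point does not remove the problem, because the text still prescribes the adjustment below 50%. Nor is this detail left to the SAP: the protocol prints both definitions, and they disagree.

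**Conclusion.** Wrong as written. Stage 2 has one definition in the weight and another in z2, and the literal z2 rule can make the adjusted p-value too small.

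On full overlap, with z1 taken at Week 24 and an assumed correlation of 0.5 to 0.8, the two-sided error is about 6.7% to 8.6% against 5%. The excess is in the tail declaring radiofrequency worse. Smaller overlap gives smaller inflation, and z1 based only on Week 52 values gives none. The correlation, the extent of overlap and the number of subjects awaiting analysis are assumptions; the protocol gives none of them. On the enrolment-date reading, with n1 limited to subjects analysed, the harm is lost power and a departure from ITT.

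This should be corrected before interim results are unblinded.

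**What to change.** In section 12.5.3.2, and in the SAP to match:

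1. Define both stages by subject. Stage 1 is the subjects whose data entered the interim. Stage 2 is every other randomised subject, including those already randomised at that time.
2. Compute z1 and z2 at the end of the study, each from its own group's Week 52 KOOS change, and count n1 and n2 on the same two groups.
3. Fix f2 in advance. It is now built from the re-calculated n2, so it could depend on the interim result, and splitting by subject alone would not then guarantee 5%.
4. State which KOOS visit supplies the interim score used for conditional power.
5. Reconcile the rule limiting increases to conditional power of 50% to under 80% with the use of this formula below 50%.

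The cost is a few sentences, with no added subjects or data.
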